Between 1 week and 1 month (30 days)	0 (0%)	0 (0%)	0 (0%)	0 (0%)	0 (0%)	0 (0%)
More than 1 month (30 days)	0 (0%)	0 (0%)	0 (0%)	0 (0%)	0 (0%)	0 (0%)
Severity						
Mild	0 (0%)	0 (0%)	0 (0%)	0 (0%)	0 (0%)	0 (0%)
Moderate	0 (0%)	0 (0%)	0 (0%)	0 (0%)	0 (0%)	0 (0%)
Severe	0 (0%)	0 (0%)	0 (0%)	0 (0%)	0 (0%)	0 (0%)
Causality						
Treatment-related*	0 (0%)	0 (0%)	0 (0%)	0 (0%)	0 (0%)	0 (0%)
Not treatment-related	0 (0%)	0 (0%)	0 (0%)	0 (0%)	0 (0%)	0 (0%)
Outcome						
Resolved	0 (0%)	0 (0%)	0 (0%)	0 (0%)	0 (0%)	0 (0%)
Improved	0 (0%)	0 (0%)	0 (0%)	0 (0%)	0 (0%)	0 (0%)
Stabilized	0 (0%)	0 (0%)	0 (0%)	0 (0%)	0 (0%)	0 (0%)
Worsened	0 (0%)	0 (0%)	0 (0%)	0 (0%)	0 (0%)	0 (0%)
Unchanged	0 (0%)	0 (0%)	0 (0%)	0 (0%)	0 (0%)	0 (0%)
Treatment Required (Action Taken)						
None	0 (0%)	0 (0%)	0 (0%)	0 (0%)	0 (0%)	0 (0%)
Study treatment interrupted/discontinued	0 (0%)	0 (0%)	0 (0%)	0 (0%)	0 (0%)	0 (0%)
Non-drug therapy	0 (0%)	0 (0%)	0 (0%)	0 (0%)	0 (0%)	0 (0%)
New OTC or Rx drug added	0 (0%)	0 (0%)	0 (0%)	0 (0%)	0 (0%)	0 (0%)
Hospitalized (includes ER visits)	0 (0%)	0 (0%)	0 (0%)	0 (0%)	0 (0%)	0 (0%)

¹ Denominator is the number of subjects who received the corresponding treatment.

² Denominator is the number of adverse events reported by subjects who received the corresponding treatment.

*Treatment-related includes Possibly and Probably Related.

For Severity and Causality, subjects reporting more than one TEAE related to vascular injections/visual event associated with a treatment arm are counted only once for the treatment arm under the greatest reported severity and most likely causality, respectively.

For Duration, Outcome and Treatment Required (Action Taken), at each level of the categories, subjects reporting more than one TEAE related to vascular injections/visual event associated with a treatment arm are counted only once for the treatment arm at that category level.

Source: Listing 16.2.7.1.1

O:\Studies\Prolenium\SYM 2018-03\Biometrics\Programs\Tables\xxx.sas ran on Month Day, Year at hh:mm on data from Month Day, Year.

Note:

Tables 14.3.2.1, 14.3.2.2, 14.3.2.3, 14.3.2.4 will be used as the shell for the following tables:

Table 14.3.3.1 – Treatment-Emergent Adverse Events (TEAEs) Excluding Vascular Injections/Visual Events by MedDRA System Organ Class and Preferred Term

Table 14.3.3.2 – Treatment-Emergent Adverse Events (TEAEs) Excluding Vascular Injections/Visual Events by MedDRA System Organ Class, Preferred Term, and Severity

Table 14.3.3.3 – Treatment-Emergent Adverse Events (TEAEs) Excluding Vascular Injections/Visual Events by MedDRA System Organ Class, Preferred Term, and Causality

Table 14.3.3.4 – Treatment-Emergent Adverse Events (TEAEs) Excluding Vascular Injections/Visual Events by MedDRA System Organ Class, Preferred Term, and Number of Injections

With footnote regarding data source change to “Source: Listing 16.2.7.1.2”.

Table 14.3.4.1 – Lip Function and Lip Sensation Tests by Visit

Study Visit	Category	PRO 2018-02 PN40082	PRO 2018-02 Restylane Silk	Total
Was the subject able to sip liquid through a straw?				
Visit 1/Day 1 (Prior to injection)	N	0	0	0
	n (%) Yes	0 (0%)	0 (0%)	0 (0%)
Visit 2/Month 1	N	0	0	0
	n (%) Yes	0 (0%)	0 (0%)	0 (0%)
Visit 3/Month 2	N	0	0	0
	n (%) Yes	0 (0%)	0 (0%)	0 (0%)
Was the subject able to feel sensation of a 0.4G monofilament at three points on the upper lip and three points on the lower lip?				
Visit 1/Day 1 (Prior to injection)				
...				
Was the subject able to feel sensation of a cotton wisp at three points on the upper lip and three points on the lower lip?				
Visit 1/Day 1 (Prior to injection)				
...				

Source: Listing 16.2.4.8

O:\Studies\Prollenium\SYM 2018-03\Biometrics\Programs\Tables\xxx.sas ran on Month Day, Year at hh:mm on data from Month, Day, Year.

Table 14.3.4.2 – Lip Texture Evaluation by Visit

Study Visit	Category	PRO 2018-02 PN40082	PRO 2018-02 Restylane Silk	Total
Visit 1/Day 1 (Prior to injection)	N	0	0	0
	n (%) Normal	0 (0%)	0 (0%)	0 (0%)
	n (%) Abnormal	0 (0%)	0 (0%)	0 (0%)
	- n (%) Abnormal: Mild	0 (0%)	0 (0%)	0 (0%)
	- n (%) Abnormal: Moderate	0 (0%)	0 (0%)	0 (0%)
	- n (%) Abnormal: Severe	0 (0%)	0 (0%)	0 (0%)
Visit 2/Month 1	...			
	...			
Visit 3/Month 2				

Source: Listing 16.2.4.9

O:\Studies\Prolenium\SYM 2018-03\Biometrics\Programs\Tables\xxx.sas ran on Month Day, Year at hh:mm on data from Month, Day, Year.

Note:

Table 14.3.4.2 will be used as the shell for the following table:

Table 14.3.4.3 – Lip Firmness Evaluation by Visit

Table 14.3.4.4 – Lip Symmetry Evaluation by Visit

Table 14.3.4.5 – Lip Movement/Function Evaluation by Visit

Study Visit	Category	PRO 2018-02 PN40082	PRO 2018-02 Restylane Silk	Total
Visit 1/Day 1 (Prior to injection)	N	0	0	0
	n (%) Normal – Subject’s ability to pucker lips	0 (0%)	0 (0%)	0 (0%)
	n (%) Normal – Subject’s ability to blow with lips	0 (0%)	0 (0%)	0 (0%)
	n (%) Normal – Subject’s ability to pronounce words that begin with “W”	0 (0%)	0 (0%)	0 (0%)
Visit 2/Month 1	...			
	...			
Visit 3/Month 2				

Source: Listing 16.2.4.8
 O:\Studies\Prolenium\SYM 2018-03\Biometrics\Programs\Tables\xxx.sas ran on Month Day, Year at hh:mm on data from Month, Day, Year.

Subject Listings

Listing 16.2.1.1 – Subject Disposition

Site-Subject	Treatment in PRO 2018-02	Subject Disposition	Date Completed or Discontinued	Reason, if discontinued
--------------	-----------------------------	---------------------	-----------------------------------	-------------------------

O:\Studies\ Prolenium\SYM 2018-03\Biometrics\Programs\Listing\xxx.sas ran on Month Day Year at hh mm on data from Month Day, Year.

Listing 16.2.1.2 – Dates of Visits

Site-Subject	Treatment in PRO 2018-02	Visit 1/ Day 1 (Baseline)	Telephone Call Day 3 (±2 days) [Day #]	Telephone Call Day 14 (±2 days) [Day #]	Visit 2/ Month 1 Day 28 (±2 days) [Day #]	Visit 3/ Month 2 Day 56 (±4 days) [Day #]	Telephone Call Day 168 (±7 days) [Day #]	No. of UVs: Unscheduled Visit(s) [Day #]
--------------	--------------------------	---------------------------------	--	---	---	---	--	--

Day # (Study Days) = Visit Date - Baseline (Visit 1) Date +1.

O:\Studies\ Prollenium\SYM 2018-03\Biometrics\Programs\Listing\xxx.sas ran on Month Day Year at hh mm on data from Month Day, Year.

Listing 16.2.2.1 – Informed Consent and Inclusion/Exclusion Criteria

Site-Subject	Treatment in PRO 2018-02	Subject signed informed consent form (ICF)?	Date ICF Signed	Inclusion #1	Inclusion #2	Inclusion #3	Exclusion #1
--------------	-----------------------------	--	-----------------	--------------	--------------	--------------	--------------

O:\Studies\ Prollenium\SYM 2018-03\Biometrics\Programs\Listing\xxx.sas ran on Month Day Year at hh mm on data from Month Day, Year.

Listing 16.2.2.2 – Comments

Site-Subject	Treatment in PRO 2018-02	Date of Comments	CRF Page Number	Comment(s)	Initials
--------------	-----------------------------	------------------	--------------------	------------	----------

O:\Studies\ Prollenium\SYM 2018-03\Biometrics\Programs\Listing\xxx.sas ran on Month Day Year at hh mm on data from Month Day, Year.

Listing 16.2.4.1 – Demographics

Site- Subject	Subject Initials	Treatment in PRO 2018-02	Age (yrs)	Sex	Race	Ethnicity	Fitzpatrick Skin Type
------------------	---------------------	-----------------------------	-----------	-----	------	-----------	-----------------------

O:\Studies\ Prolenium\SYM 2018-03\Biometrics\Programs\Listing\xxx.sas ran on Month Day Year at hh mm on data from Month Day, Year.

Listing 16.2.4.2 – Brief Physical Examination at Baseline

Site-Subject	Treatment in PRO 2018-02	Height (inches)	Weight (lbs)	Physical Examination		
				Heart	Lungs	Abdomen

O:\Studies\ Prolenium\SYM 2018-03\Biometrics\Programs\Listing\xxx.sas ran on Month Day Year at hh mm on data from Month Day, Year.

Listing 16.2.4.3 – Medical History Findings

Site-Subject	Treatment in PRO 2018-02	Medical System	Diagnosis/Procedure	Onset Date	Stop Date	Concomitant Medication?
		xxxxxxx	xxxxxxxxxxxxx	----1997	Ongoing	No

O:\Studies\ Prollenium\SYM 2018-03\Biometrics\Programs\Listing\xxx.sas ran on Month Day Year at hh mm on data from Month Day, Year.

Listing 16.2.4.4 – Prior and Concomitant Medications/Treatments

Site-Subject	Treatment in PRO 2018-02	If Used on Face	WHO Class // WHO Name // Medication	Indication	Start Date [Day #]	Stop Date [Day #]	Dosage	Freq.	Route
		QD1	XXXXXXXXXX // XXXXXXXXXXXXX XXX // XXXXXXXXXXXX XXXXXXXXXX		01JAN05 [3]	Ongoing	xxxxx	xxxx	xxx

Note: Medications coded using the WHO Drug Dictionary, version xxx.

Day # is calculated from baseline (Visit 1) date. Day 1 is the baseline date while Day -1 is the day prior to the baseline visit. L=Left side of the face, R=Right side of the face.

O:\Studies\ Prollenium\SYM 2018-03\Biometrics\Programs\Listing\xxx.sas ran on Month Day Year at hh:mm on data from Month Day, Year.

Listing 16.2.4.5 – Non-Pharmacological Interventions (NPIs)

Site-Subject	Treatment in PRO 2018-02	If Used on Face	Non-Pharmacological Intervention	Indication	Start Date [Day #]	Stop Date [Day #]	Dosage	Freq.	Route
		QD1,QD2	XXXXXXXXXX XXX XXXXXXXXXXX	XXXXXXXX	01JAN05 [3]	Ongoing	xxxxx	xxxx	xxx

Day # is calculated from baseline (Visit 1) date. Day 1 is the baseline date while Day -1 is the day prior to the baseline visit. L=Left side of the face, R=Right side of the face.
 O:\Studies\ Prollenium\SYM 2018-03\Biometrics\Programs\Listing\xxx.sas ran on Month Day Year at hh:mm on data from Month Day, Year.

Listing 16.2.4.6 – Vital Signs and Urine Pregnancy Test at Baseline

Site- Subject	Treatment in PRO 2018-02	Sitting Systolic BP (mmHg)	Sitting Diastolic BP (mmHg)	Heart Rate (bpm)	Oral Temperature (°F)	Respiratory Rate (breath/min)	Urine Pregnancy Test	
							Test Results	Test Date

O:\Studies\ Prollenium\SYM 2018-03\Biometrics\Programs\Listing\xxx.sas ran on Month Day Year at hh mm on data from Month Day, Year.

Listing 16.2.4.7 – Vision Evaluation

Site- Subject	Treatment in PRO 2018-02	Study Visit (Time Point)	Subject wearing corrective lenses?	Confrontational Visual Field Results (Specify if abnormal), Assessed by	Ocular Visual Field Results (Specify if abnormal), Assessed by	Snellen Visual Acuity Score (SVAS)		SVAS Assessed by	Vision at Post-Baseline Visit	
						Left Eye	Right Eye		Changed significantly from PRO 2018-02 baseline?	If yes, the study ophthalmologist contacted?

O:\Studies\ Prolenium\SYM 2018-03\Biometrics\Programs\Listing\xxx.sas ran on Month Day Year at hh mm on data from Month Day, Year.

Listing 16.2.4.8 – Lip Function, Lip Sensation and Lip Movement/Function Tests

Site- Subject	Treatment in PRO 2018-02	Study Visit (Time Point)	Able to sip liquid through a straw?	Assessor of Lip Function	Able to feel sensation of a cotton wisp?	Able to feel sensation of a 0.4G monofilament	Assessor of Lip Sensation	Ability to pucker lips	Ability to blow with lips	Ability to pronounce words that begin with “W”	Assessor of Lip Movement /Function
------------------	-----------------------------	-----------------------------	--	--------------------------------	---	--	---------------------------------	------------------------------	---------------------------------	---	---

O:\Studies\ Prolenium\SYM 2018-03\Biometrics\Programs\Listing\xxx.sas ran on Month Day Year at hh mm on data from Month Day, Year.

Listing 16.2.4.9 – Lip Texture, Lip Firmness and Lip Symmetry Evaluations

Site- Subject	Treatment in PRO 2018-02	Study Visit (Time Point)	Lip Texture		Lip Firmness		Lip Symmetry	
			Normal or Abnormal (severity)	Evaluator	Normal or Abnormal (severity)	Evaluator	Normal or Abnormal (severity)	Evaluator

O:\Studies\ Prollenium\SYM 2018-03\Biometrics\Programs\Listing\xxx.sas ran on Month Day Year at hh mm on data from Month Day, Year.

Listing 16.2.5.1 – Treatment Administration at Visit 1/Day 1

Site-Subject	Treatment in	Injection placed successfully?	Site of Injection	Time of Injection	Amount of Syringe Used (ml)	Injection Techniques Used	Depth of Injection	Initials Who Performed Injection	Investigator Ease of Use Assessment	Evaluator
--------------	--------------	--------------------------------	-------------------	-------------------	-----------------------------	---------------------------	--------------------	----------------------------------	-------------------------------------	-----------

Investigator Ease of Use Assessment assess on the Numerical Rating Scale (NRS): 0 (Not Easy) to 10 (Most Easy).

O:\Studies\ Prollenium\SYM 2018-03\Biometrics\Programs\Listing\xxx.sas ran on Month Day Year at hh mm on data from Month Day, Year.

Listing 16.2.6.1 – Efficacy Evaluations of Lip Fullness Grading Scale and Perioral Lines at Rest Severity Scale

Site- Subject	Treatment in PRO 2018-02	Study Visit	Lip Fullness Grading Scale (LFGS) Rating				Perioral Lines at Rest Severity Scale (POL)			
			Overall Rating	Upper Lip Rating	Lower Lip Rating	Assessed by	Overall Rating	Upper Lip Rating	Lower Lip Rating	Assessed by
xx-xxx	R. Silk	Visit 1 (PRO 2018-02) Visit 1 (Retreatment)								

O:\Studies\ Prolenium\SYM 2018-03\Biometrics\Programs\Listing\xxx.sas ran on Month Day Year at hh mm on data from Month Day, Year.

Listing 16.2.6.2 – Efficacy Evaluations of Subject Satisfaction with Lips, Swelling and Global Aesthetic Improvement

Site- Subject	Treatment in PRO 2018-02	Study Visit	Subject Satisfaction with Lips VAS	Swelling Assessment		Patient Global Aesthetic Improvement (pGAI)	Investigator Global Aesthetic Improvement (iGAI)	
				Grade	Performed By		Score	Performed By

O:\Studies\ Prollenium\SYM 2018-03\Biometrics\Programs\Listing\xxx.sas ran on Month Day Year at hh mm on data from Month Day, Year.

Listing 16.2.7.1.1 – Adverse Events (Related to Vascular Injections/Visual Events)

Site-Subject	Trt. in PRO	FST	Reported by	System Organ Class// Preferred Term// Verbatim Term	Start Date Time [Day #]	Stop Date Time [Day #]	Severity Causality Outcome	Where on face Rel. to injection? Vision related?	Action Taken ¹	SAE
xx-xxx	R. Silk	III	Subj/Diary	GENERAL DISORDERS AND ADMINISTRATION SITE CONDITIONS// INJECTION SITE SWELLING// SWELLING ON FACE	01JAN2019 13:25 2	04JAN2019 08:30 5	MILD PROBABLY STABLIZED	QD1, QD3 Y N	3,4	N

Day # is calculated from baseline (Visit 1) date. Day 1 is the baseline date while Day -1 is the day prior to the baseline visit.

¹ Action Taken: 1=None, 2=Study treatment interrupted/discontinued, 3=Non-drug therapy, 4=New OTC or Rx drug added, 4=Hospitalized

O:\Studies\ Prollenium\SYM 2018-03\Biometrics\Programs\Listing\xxx.sas ran on Month Day Year at hh mm on data from Month Day, Year.

Listing 16.2.7.1.2 – Adverse Events (Excluding Vascular Injections/Visual Events)

Site-Subject	Trt. in PRO	FST	Reported by	System Organ Class// Preferred Term// Verbatim Term	Start Date [Day #]	Stop Date [Day #]	Severity Causality Outcome	Where on face	Action Taken ¹	SAE
xx-xxx	R. Silk	III	Subj/Diary	NERVOUS SYSTEM DISORDERS// HEADACHE // HEADACHE	01JAN2019 2	04JAN2019 5	MILD UNLIKELY STABLIZED	QD1,QD3	1	N

Day # is calculated from baseline (Visit 1) date. Day 1 is the baseline date while Day -1 is the day prior to the baseline visit.

¹ Action Taken: 1=None, 2=Study treatment interrupted/discontinued, 3=Non-drug therapy, 4=New OTC or Rx drug added, 4=Hospitalized

O:\Studies\ Prolenium\SYM 2018-03\Biometrics\Programs\Listing\xxx.sas ran on Month Day Year at hh mm on data from Month Day, Year.

Note:

Repeat Listings 16.2.7.1.1 and 16.2.7.1.2 for AEs that led to study treatment interrupted/Discontinued and Serious AEs –

Listing 16.2.7.2.1 – Adverse Events (Related to Vascular Injections/Visual Events) Leading to Study Treatment Interrupted/Discontinued

Listing 16.2.7.2.2 – Adverse Events (Excluding Vascular Injections/Visual Events) Leading to Study Treatment Interrupted/Discontinued

Listing 16.2.7.3.1 – Serious Adverse Events (Related to Vascular Injections/Visual Events)

Listing 16.2.7.3.2 – Serious Adverse Events (Excluding Vascular Injections/Visual Events)

Listing 16.2.7.4 – Adverse Events (Related to Vascular Injections/Visual Events) Lasted more than 30 Days

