Number of Subjects: Eligible subjects from the PRO 2018-02 study will be encouraged to be retreated. It is anticipated that the number of subjects will be less than the 158 subjects enrolled in the PRO 2018-02 study.

Inclusion Criteria:

1. In Protocol PRO 2018-02, met all inclusion/exclusion criteria; received study device, completed Visit 5 within the specified window; had LFGS score by the Blinded Evaluating Investigator at Visit 3/Month 2 within the specified visit window, and had no significant protocol violations that would affect the treatment evaluation.
2. If female and of childbearing potential, a negative urine pregnancy test at Visit 1/Day 1 and the subject agrees to use adequate contraception during the study period.
3. Willing to give written informed consent

Exclusion Criteria:

1. Women who are pregnant, lactating, or planning a pregnancy

Study Device

PN40082: a clear, colorless gel in 1.0 mL pre-filled syringes with 25 mg/mL of stabilized hyaluronic acid and lidocaine 0.3% w/w

Statistical Methods

Safety and efficacy results will be summarized descriptively for all subjects who receive retreatment in this study. Data will be summarized overall and also broken down by the treatment arm in PRO 2018-02.

Efficacy Analysis:

Change from baseline in this study and change from baseline in the prior controlled study will be summarized for LFGS and POL. Other efficacy variables include pGAI, iGAI, and Swelling Assessment at Visit 3/Month 2.

Safety Analysis:

Adverse events will be coded to system organ class and preferred terms using the Medical Dictionary for Regulatory Activities (MedDRA, Version 20 or higher).

Frequency and percentage of subjects reporting treatment-emergent adverse events (TEAEs) will be tabulated overall and for each treatment in PRO 2018-02 by preferred terms and further by severity and relationship to study device. In summaries of severity and relationship, subjects reporting more than one event in a treatment arm that are mapped to the same preferred term will be counted only once in that treatment arm under the strongest severity and relationship, respectively. In addition, visual-related TEAEs will be summarized separately by preferred term.

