8.3 Safety Analysis

Adverse events will be coded to system organ class and preferred terms using the Medical Dictionary for Regulatory Activities (MedDRA, Version 20 or higher).

Frequency and percentage of subjects reporting TEAEs will be tabulated overall and for each treatment in PRO 2018-02 by preferred terms and further by severity and relationship to study device. In summaries of severity and relationship, subjects reporting more than one event in a treatment arm that are mapped to the same preferred term will be counted only once in that treatment arm under the strongest severity and relationship, respectively. In addition, visual related TEAEs will be summarized separately by preferred term.

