Listing 16.2.4.4 – Prior and Concomitant Medications/Treatments	42
Listing 16.2.4.5 – Non-Pharmacological Interventions (NPIs)	43
Listing 16.2.4.6 – Vital Signs and Urine Pregnancy Test at Baseline	44
Listing 16.2.4.7 – Vision Evaluation.....	45
Listing 16.2.4.8 – Lip Function, Lip Sensation and Lip Movement/Function Tests	46
Listing 16.2.4.9 – Lip Texture, Lip Firmness and Lip Symmetry Evaluations	47
Listing 16.2.5.1 – Treatment Administration at Visit 1/Day 1	48
Listing 16.2.6.1 – Efficacy Evaluations of Lip Fullness Grading Scale and Perioral Lines at Rest Severity Scale	49
Listing 16.2.6.2 – Efficacy Evaluations of Subject Satisfaction with Lips, Swelling and Global Aesthetic Improvement.....	50
Listing 16.2.7.1.1 – Adverse Events (Related to Vascular Injections/Visual Events).....	51
Listing 16.2.7.1.2 – Adverse Events (Excluding Vascular Injections/Visual Events).....	52
Listing 16.2.7.2.1 – Adverse Events (Related to Vascular Injections/Visual Events) Leading to Study Treatment Interrupted/Discontinued	52
Listing 16.2.7.2.2 – Adverse Events (Excluding Vascular Injections/Visual Events) Leading to Study Treatment Interrupted/Discontinued	52
Listing 16.2.7.3.1 – Serious Adverse Events (Related to Vascular Injections/Visual Events).....	52
Listing 16.2.7.3.2 – Serious Adverse Events (Excluding Vascular Injections/Visual Events).....	52
Listing 16.2.7.4 – Adverse Events (Related to Vascular Injections/Visual Events) Lasted more than 30 Days	52

Statistical Analysis Plan

1 Purpose of Statistical Analysis Plan

The purpose of the statistical analysis plan is to describe in detail all the data, statistical methods, and summary tables required to implement the statistical analysis of Clinical Study Protocol PRO 2018-03 (Section 8 in the study protocol version 2.0, dated November 13, 2018).

2 Study Objectives

To evaluate the safety and efficacy of retreatment with PN40082 for lip augmentation.

3 Study Design and Sample Size Determination

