5.6 Safety Variables

Key safety variables include incidence rate of treatment-emergent adverse events (TEAEs) and the exposure to the study product, as well as Investigator Ease of Use Assessment, lip function, lip sensation, lip texture, lip firmness, lip symmetry, and lip movement/function.

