5.6.1 Adverse Events

All adverse events (AEs) occurring during the study will be recorded and coded in the Medical Dictionary for Regulatory Activities (MedDRA), version 20 or higher. TEAEs are defined as events that appear subsequent to the open-label injection or that were present prior to the open-label injection but worsened in intensity after the open-label injection.

TEAEs (those related to vascular injections/Visual events, separate from those that were not related to vascular injections/Visual events) for the retreated subjects will be summarized grouped by the number of injections that were received of PN40082, or Restylane Silk during the prior controlled study (PRO 2018-02). Frequency and percent of subjects reporting TEAEs of injection site will be tabulated by preferred terms, and further by severity and relationship to study device. In summaries of severity and relationship, subjects who reported more than one event in a treatment arm that are mapped to the same preferred term will be counted only once in that treatment arm under the strongest severity and relationship, respectively.

TEAEs related to vascular injections/Visual events will also be tabulated by subject Fitzpatrick Skin Type (I-III vs. IV-VI), each Fitzpatrick Skin Type individually and by number of injections subjects received.

Treatment-Emergent Serious Adverse Events (TESAEs) and TEAEs that led to treatment interruption or discontinuation will be presented in data listings.

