5.6.3 Other Variables

Investigator Ease of Use Assessment

Overall ease of use of the device will be evaluated by the Treating Investigator using the numerical rating scale (NRS) from 0 being not easy to 10 being most easy at Visit 1/Day. It will be summarized for all retreated subjects descriptively with mean, SD, minimum, median, and maximum.

Lip Evaluations

Lip function, lip sensation, lip texture, lip firmness, lip symmetry, and lip movement/function will be evaluated by the Blinded Evaluating Investigator at each visit. These variables will be summarized using frequency and percent of subjects by categories of incidence.

Concomitant Medications

Concomitant medications will be coded using the World Health Organization (WHO) Drug Dictionary, Version March 2013 or later, and will be presented in data listings.

6 Tables and Listings

The following is an example of tables and listings that will be included in the clinical study report. Tables and listings may be modified as needed during the data analyses.

7 Appendices

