Amount of Syringe Used (ml)	N	0	0	0
	Mean ± SD	0.0 ± 0.00	0.0 ± 0.00	0.0 ± 0.00
	Median	0.0	0.0	0.0
	Min, Max	0, 0	0, 0	0, 0
Injection Techniques Used	N (%) Serial Puncture	0 (0.0%)	0 (0.0%)	0 (0.0%)
	N (%) Antegrade Linear Threading	0 (0.0%)	0 (0.0%)	0 (0.0%)
	N (%) Retrograde Linear Threading	0 (0.0%)	0 (0.0%)	0 (0.0%)
Depth of Injection	N (%) Submucosa	0 (0.0%)	0 (0.0%)	0 (0.0%)
	N (%) Intramuscular	0 (0.0%)	0 (0.0%)	0 (0.0%)
	N (%) Superficial Dermis	0 (0.0%)	0 (0.0%)	0 (0.0%)
	N (%) Mid Dermis	0 (0.0%)	0 (0.0%)	0 (0.0%)
	N (%) Deep Dermis	0 (0.0%)	0 (0.0%)	0 (0.0%)
	N (%) Subcutaneous Fat	0 (0.0%)	0 (0.0%)	0 (0.0%)
	Investigator Ease of Use Assessment	Mean ± SD	0.0 ± 0.00	0.0 ± 0.00
Median		0.0	0.0	0.0
Min, Max		0, 0	0, 0	0, 0

Investigator Ease of Use Assessment based on the Numerical Rating Scale (NRS): 0 (Not Easy) to 10 (Most Easy).

Source: Listing 16.2.5.1

O:\Studies\Prollenium\SYM 2018-03\Biometrics\Programs\Tables\xxx.sas ran on Month Day, Year at hh:mm on data from Month, Day, Year.

Note:

Table 14.3.1.1 will be used as the shell for the following table:

Table 14.3.1.2 – Exposure to Study Product and Investigator Ease of Use Assessment (Lower Lips) at Visit 1/Day 1 Retreatment

Table 14.3.1.3 – Exposure to Study Product and Investigator Ease of Use Assessment (Perioral Areas) at Visit 1/Day 1 Retreatment

Table 14.3.2.1 – Treatment-Emergent Adverse Events (TEAEs) Related to Vascular Injections/Visual Events by MedDRA System Organ Class and Preferred Term

System Organ Class Preferred Term	Reported by Subject or PI	PRO 2018-02	PRO 2018-02	Total (N=xx)
		PN40082 (N=xx)	Restylane Silk (N=xx)	
Subjects with at Least One Injection-Site or Visual TEAE	By Subject	0 (0%)	0 (0%)	0 (0%)
	By PI	0 (0%)	0 (0%)	0 (0%)
	Total	0 (0%)	0 (0%)	0 (0%)
Class 1	By Subject	0 (0%)	0 (0%)	0 (0%)
	By PI	0 (0%)	0 (0%)	0 (0%)
	Total	0 (0%)	0 (0%)	0 (0%)
Term 1	By Subject	0 (0%)	0 (0%)	0 (0%)
	By PI	0 (0%)	0 (0%)	0 (0%)
	Total	0 (0%)	0 (0%)	0 (0%)
...				
...				

Counts reflect numbers of subjects reporting one or more TEAE related to vascular injections/visual event that map to the MedDRA (version x x) system organ class/preferred term. At each level of summarization (system organ class or preferred term), subjects reporting more than one event are counted only once.

Source: Listing 16.2.7.1.1

O:\Studies\Prolenium\SYM 2018-03\Biometrics\Programs\Tables\xxx.sas ran on Month Day, Year at hh:mm on data from Month Day, Year.

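### The protocol requires visual TEAEs to be summarized separately by preferred term, but SAP 5.6.1 and all 13 adverse-event shells only pool them in a class that appears to include routine injection-site reactions

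*SAP*

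**What the plan says.** Protocol 8.3, after setting out the general TEAE tabulation, adds: "In addition, visual related TEAEs will be summarized separately by preferred term". The synopsis says the same. SAP section 1 gives the SAP's purpose as to "describe in detail all the data, statistical methods, and summary tables required to implement the statistical analysis of Clinical Study Protocol PRO 2018-03", and points to protocol section 8.

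SAP 5.6.1 organizes the adverse-event tables differently. It splits TEAEs in two: "TEAEs (those related to vascular injections/Visual events, separate from those that were not related to vascular injections/Visual events". The next sentence plans a tabulation of injection-site TEAEs by preferred term, severity and relationship. No sentence plans a summary of visual events alone, and none says how an event is assigned to one side of the split or the other.

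The shells follow the split. Tables 14.3.2.1 to 14.3.2.9 cover the vascular/visual class; Tables 14.3.3.1 to 14.3.3.4 cover the rest. In Tables 14.3.2.1, .2, .3 and .5 the leading row is "Subjects with at Least One Injection-Site or Visual TEAE". Listing 16.2.7.1.1, the source for the first set, has one column for relation to the injection and another headed *Vision related?*.

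SAP 5.6 also states: "Key safety variables include incidence rate of treatment-emergent adverse events (TEAEs".

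**The concern.** Vision change is one of the two kinds of event that Protocol 7.9.3.4 singles out for immediate reporting, and the protocol commits to showing visual TEAEs by themselves. Followed as written, the SAP would leave out that summary.

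The class that replaces it also seems to be mislabelled. If it holds ordinary injection-site reactions, then bruising and swelling, which Protocol 7.9.3.1 treats as expected, would be reported under a title that suggests intravascular injection or a visual complication. The leading row would then say little about vision.

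The missing assignment rule has a practical effect. It decides which events get the extra tables on skin type, most frequent terms, duration, and outcome and action taken (14.3.2.5 to 14.3.2.9), and which get only the four basic ones.

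**Working it through.** The study is descriptive and states no figure on this point, so the check is a comparison of requirement and plan, followed by what can and cannot be read from the planned rows.

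**Step 1. Count the shells.** 9 (14.3.2.1 to .9) + 4 (14.3.3.1 to .4) = 13 adverse-event shells.

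| Shells | Content | Limited to visual TEAEs |
|---|---|---|
| 14.3.2.1 to .5 (5) | every preferred term in the class, no cut-off | 0 |
| 14.3.2.6 to .8 (3) | only terms reported by at least 5% of retreated subjects | 0 |
| 14.3.2.9 (1) | class totals, no preferred terms | 0 |
| 14.3.3.1 to .4 (4) | the complement | 0 |

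The required visual-only summary is in 0 of 13 shells, and the text of 5.6.1 does not plan it either. The front part of the SAP's table list is not in the text available, but the bodies of all these shells are.

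**Step 2. What is in the class?** The evidence, in order of weight:
- The leading row in four shells names injection-site events and visual events as alternatives.
- 5.6.1 moves from the split straight to injection-site TEAEs.
- The example record in Listing 16.2.7.1.1 is a mild injection-site swelling marked as related to the injection and not related to vision. It is template text and carries little weight.

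Together these point to a class of injection-site or visual events. That is an inference. If instead the class is meant to be truly vascular or visual, the row label and the example are wrong, and visual events are still pooled with vascular ones. A separate visual summary is missing either way.

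**Step 3. What can be seen of visual events as planned.** Each visual term is a row in Tables 14.3.2.1 to .5, and the listing flags each event. In Tables 14.3.2.6 to .8 a rare visual term drops out by design. The synopsis expects fewer than 158 subjects; at N = 157 the threshold is 0.05 × 157 = 7.85, so 8 subjects.

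**Step 4. What the rows do not give.** The footnote to Table 14.3.2.1 reads: "At each level of summarization (system organ class or preferred term), subjects reporting more than one event are counted only once". Rows therefore count subjects, and one subject may be in several. With v₁, v₂, … subjects in the visual rows, the number V with any visual TEAE is known only to satisfy

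max(vⱼ) ≤ V ≤ min(N, Σvⱼ).

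A system-organ-class row would give V only if all visual terms fell in one class that held nothing else; the documents do not say so. Similarly, with a subjects in the vascular/visual class and b in the complement, the number T with any TEAE satisfies

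max(a, b) ≤ T ≤ min(N, a + b),

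because the same subject may be in both.

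**Step 5. Carry-over into the complement.** Tables 14.3.3.1 to .4 reuse shells 14.3.2.1 to .4, with only the source footnote changed. The injection-site-or-visual row is therefore carried into 14.3.3.1, .2 and .3, which are meant to exclude such events. Shell 14.3.2.4 has no such row, so 14.3.3.4 is not affected by it.

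**The case against.** The strongest reply is that the shells are only examples. SAP section 6 says: "Tables and listings may be modified as needed during the data analyses". That stands to this extent: absence from a shell alone would be weak evidence, and correction is easy. But the text of 5.6.1 also lacks the summary, and permission to modify tables neither plans the summary nor supplies the assignment rule.

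Second, the class is not wholly obscure. The row label, the injection-site sentence and the two listing columns together suggest a rule under which either flag places an event in the class. That is fair. What remains is that the rule is unwritten and the titles do not match it.

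Third, the risk of misreading is limited. Tables 14.3.2.1 to .8 print preferred terms, so injection-site swelling would appear by name. Only Table 14.3.2.9 gives class totals without terms. This stands.

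Stronger readings are tempting, and the documents do not support them:
- A reader might infer that visual events would be lost or hidden. They would not: they have their own rows in five tables and a flag in the listing.
- A reader might infer that the protocol requires a count of subjects with any visual TEAE, or with any TEAE. Protocol 8.3 asks for a separate visual summary by preferred term; its word overall refers to the prior arms combined. SAP 5.6 names TEAE incidence as a key variable but does not promise it as one figure, and both counts can be obtained from the by-subject listings.
- A reader might take the visual symptoms named in Protocol 7.9.3.4 as a ceiling on how many rows one subject could occupy. That list is expressly open-ended, and its coding is not given, so no ceiling follows.

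**Conclusion.** The point holds as a mismatch between protocol and SAP: the protocol specifies a separate visual summary, and neither 5.6.1 nor any of the 13 shells provides it. This needs no assumption and is certain on the text.

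That the pooled class contains routine injection-site reactions is well supported but inferred. On that reading the table titles do not describe their content.

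The consequence is moderate. A safety summary that the protocol promises would be missing, and ordinary reactions would stand under a vascular/visual title. No data are lost and no inferential result depends on it. It should be fixed before database lock, the deadline Protocol section 8 sets for a final SAP. The two subject-level counts are good practice, not omissions from a requirement.

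**What to change.** Needed:
1. Add one TEAE table limited to visual events, by preferred term, by prior arm and in total, with no 5% cut-off, using the *Vision related?* field. That field is in Listing 16.2.7.1.1 only, so the rule in item 2 should send every vision-related event to that class.
2. State in SAP 5.6.1 the rule that assigns an event to the class, for example by the two listing flags. Make the titles, header rows and footnotes of Tables 14.3.2.x and 14.3.3.x agree with it, and remove the header row carried into Tables 14.3.3.1 to 14.3.3.3.

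Recommended, though not required by the protocol:
- In the new table, a row for subjects with at least one visual TEAE.
- One row for subjects with any TEAE, by prior arm and in total. SAP 5.6 names TEAE incidence as a key safety variable, and the two class counts cannot be added.

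The cost is one table, one sentence and corrected labels, plus two rows if the recommendations are taken up. The fields are already in the planned listings, so no new data collection is needed.
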